# 4.7 Psycho-Social Surveys

Each participant enrolled prospectively (both members of the couple) will complete an online 20-minute survey at 3 time points and the couple will receive a gift card after the last survey is completed. The three time points are:

- Two weeks after disclosure of study sequencing results or 4 weeks after enrollment for the unsequenced prenatal group
- One month after discharge from the hospital or end of the pregnancy if there is a fetal demise or pregnancy termination
- Twelve months postpartum

If the patient delivers before completion of the first survey, a survey that combines elements of the first two surveys will be administered. The measures collected at each time period are detailed in Table 3.

**Table 3. Psychosocial Survey Measures** 

Variable	Measure	Time		
		Post results/ enroll	1mth pp	12mth pp
Anxiety	Personal Health Questionnaire-8	X	X	X
Depression	General Anxiety Disorder	X	X	X
Genetic Knowledge	Adapted from measures used in CSER/eMERGE	X		
Numeracy	Adapted from measures used in CSER/eMERGE	X		
General Optimism	Life Orientation Test	X		
Tolerance with Ambiguity	Tolerance with Ambiguity	X		
Perceived control over health	Internal Health Locus of Control	X		
Genetic Essentialism	Parrott Genetic Essentialism	X		
Consenting and Education Experience	Modified Genetic Counseling Satisfaction Scale and Doctor-Patient perceptions of communication	X		
Satisfaction w/ decision to Participate	Decision Regret Scale	X	X	X
Satisfaction w/ decision to continue	Decision Regret Scale	X	X	X

Parent-Infant	Parent-Infant Attachment Questionnaire		X	X
relationship	(Reck 16 question)			
Parenting stress &	Child Vulnerability scale 54		X	X
anxiety for child	·			
Parents' experience of	Parent Sense of Competence Scale			X
parenting				
Therapeutic	Brief Illness Perception Questionnaire	X	X	X
Optimism/Prognosis				
Marital Relationship	Kansas Marital Satisfaction Scale	X	X	X
Quality of life	ITQOL:			X
	https://www.healthactchq.com/surveys.php			
COVID-19	History of maternal and infant COVID-19	X	X	X
	infection			
Study group	Reasons for joining the sequenced or	X		
	unsequenced group			
Prenatal sequencing	only			
Results Disclosure	Disclosure and non-disclosure of results to	X	X	X
and Secrecy	others			
Understanding of	Adapt from measures used in CSER/	X	X	X
Results	eMERGE			
Emotional Response	FACToR-12 (12 items)	X	X	X
to Results				
Perceptions of	PUGS perceptions of uncertainties in genetic	X	X	X
uncertainty of results	sequencing			
Impact of sequencing	Impact of sequencing results on pregnancy		X	X
results	management			

The end of the survey will have a free text box for participants to add any other details they wish to share and also ask if the participant is willing to speak by phone in a semi-structured interview (Section 4.7.1).

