# 1.3 Purpose of the Study Protocol

This protocol describes the background, design and organization of the study and may be viewed as a written agreement among the study investigators. It is approved by the funding agency (NICHD), the study Steering Committee, the Data Safety Monitoring Board (DSMB), the single Institutional Review Board (IRB) of the Clinical Coordinating Center and participating laboratories before recruitment begins. Any changes to the protocol during the study period require the approval of the Steering Committee and the IRB.

A manual of operations supplements the protocol with detailed specifications of the study procedures.

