#### 4.10.2 Secondary Outcomes (Prenatal sequencing and unsequenced prenatal)

- 1. Perinatal outcomes including gestational age at delivery, major morbidities including mechanical ventilation, sepsis, pressor support, ECMO, metabolic abnormalities (e.g., acidosis, elevated uric acid, hypo-/hyperglycemia), intraventricular hemorrhage, periventricular leukomalacia, encephalopathy, and seizure
- 2. Neonatal/infant death at time of discharge and at 12 months of age\*
- 3. Length of initial NICU stay and number of days spent in the hospital between initial discharge and 12 months of age\*
- 4. Infant weight and length at 12 months of age\*

- 5. Developmental parameters (communication, gross motor, fine motor, problem solving and personal-social) at 12 months of age using ASQ-3\*
- 6. Anxiety following result disclosure (or 4 weeks post enrollment for the unsequenced group), neonatal discharge and 12 months postpartum\*
- 7. Depression following result disclosure (or 4 weeks post enrollment for the unsequenced group), neonatal discharge and 12 months postpartum\*
- 8. Quality of life for the patient and family at 12 months postpartum\*
- 9. Incremental cost per Quality Adjusted Life Year (QALY)
- \* Only available on participants enrolled prospectively and followed through 12 months postpartum

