#### **5.3.2** Psychosocial outcomes

The secondary psychosocial outcomes are descriptive and will be reported as the observed proportion (frequency) with 95% confidence intervals. Exact confidence intervals will be reported as appropriate. All outcomes will be assessed at three time periods (post disclosure/enrollment, post discharge, and 12 months postpartum) and each time period will be analyzed separately. The initial analyses will compare prenatal sequencing (those receiving a genetic result of any type) with the prospective unsequenced prenatal group. Exploratory analyses will include pairwise comparisons between each variant classification (unsequenced prenatal group, negative sequencing result, VUS result, and pathogenic/likely pathogenic sequencing results).

Associations between the outcomes and key demographics also will be assessed. Further, association between outcomes and study groups will be tested in a multivariate setting adjusting for other variables hypothesized to affect outcome (e.g. demographics, genetic essentialism and genetic optimism). Continuous outcomes will be analyzed using a multivariate linear regression model and binary outcomes using a logistic regression model. Standard model selection methods and regression diagnostics will be performed to assess goodness of fit.

A thematic analysis will be performed for the qualitative interview data to identify patterns or themes in these data. Summary statistics will be reported for the themes.

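### Table 3 crosses the anxiety and depression instruments, and section 5.3.2 offers as an example covariate a scale measured only after disclosure in the sequenced group

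*Combined protocol and SAP*

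**What the plan says.** **Instruments.** Table 3 in section 4.7 assigns "Personal Health Questionnaire-8" to the Anxiety row and "General Anxiety Disorder" to the Depression row, each at all three surveys. Section 4.10.2 lists outcome 6 as "Anxiety following result disclosure (or 4 weeks post enrollment for the unsequenced group), neonatal discharge and 12 months postpartum" and outcome 7 as "Depression following result disclosure (or 4 weeks post enrollment for the unsequenced group), neonatal discharge and 12 months postpartum". Neither names a scale. Section 1.3 adds that "A manual of operations supplements the protocol with detailed specifications of the study procedures"; that manual is not among the documents supplied.

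**Analysis.** Section 5.3.2 says: "The secondary psychosocial outcomes are descriptive and will be reported as the observed proportion (frequency) with 95% confidence intervals". It also provides linear regression for continuous outcomes and logistic regression for binary ones. After an initial comparison of the sequenced group with the prospective unsequenced group, it plans a further model "adjusting for other variables hypothesized to affect outcome (e.g. demographics, genetic essentialism and genetic optimism").

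**Timing.** Section 4.7 places the first survey two weeks after disclosure in the sequenced group and four weeks after enrollment in the unsequenced group. A combined survey is used if delivery comes first. Table 3 schedules the genetic essentialism scale at that first survey only. Section 4.3 lists what is recorded at enrollment. It contains no attitude scale; religion and religiosity are its only belief items.

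**The concern.** Two parts of the psychosocial plan do not do what their wording suggests.

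First, an operative outcome table pairs each of two constructs with the other's instrument, and no other supplied text overrides it. A programmer who builds derived variables from Table 3 would publish anxiety results under the name of depression, and the reverse.

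Second, and of less weight, the adjusted group comparison may condition on a variable measured after the event whose impact is being studied. Aim 3 in section 1.2 sets out to assess the psychological impact of sequencing and of returning results, and speaks of parental attitudes at baseline. No survey is scheduled before disclosure in the sequenced group. If receiving a fetal result changes how parents think about genes, adjusting for that belief takes part of the impact out of the estimate. A reader of the adjusted contrast could not tell whether this had happened.

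**Working it through.** The plan states no figure on this point, so there is none to reproduce. The check sets the sections side by side.

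**Step 1: the label.** The measure in the Depression row is named for anxiety, so that row is wrong on its face. The documents do not say what the other questionnaire measures. But there are two rows and two instruments, so moving the anxiety-named one to Anxiety leaves the other for Depression. Table 3 in version 1.0 has the same pairing, with each row intact, so a fault in text extraction is unlikely.

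- Results misnamed if the table is followed: 2 outcomes × 3 time points = 6.
- Collected values changed: 0.

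**Step 2: when the example covariates are measured.** Section 5.3.2 gives three examples.

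| Example | Where recorded | Timing |
|---|---|---|
| Demographics | Section 4.3 | Enrollment |
| Genetic essentialism | Table 3 | 1 of 3 surveys: the first, after disclosure if sequenced |
| Genetic optimism | No row of that name | Probably General Optimism, "Life Orientation Test": 1 of 3 surveys, the first |

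Attitude scales listed at enrollment: 0. Belief items listed there: 2 (religion and religiosity).

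**Step 3: what adjustment does.** Assume, for illustration, a linear model with no interaction and one attitude score E:

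mean outcome = a + b·G + c·E, with G = 1 for sequenced and 0 for unsequenced.

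Let the groups differ in E by s + d, where s was present before disclosure (it goes with the choice of group) and d is the shift caused by disclosure.

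- Unadjusted group difference: b + c·(s + d).
- Difference adjusted for E: b.
- Difference due to sequencing and disclosure, including any path through attitudes: b + c·d.

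Measured against the third line, the unadjusted contrast is off by c·s (confounding by attitudes) and the adjusted contrast is off by −c·d (part of the disclosure effect removed). The documents give no value for c, s or d. If c or d is zero, adjustment removes nothing of the effect. If c·s is large, leaving attitudes out is the worse choice. An enrollment-only model removes the part of c·s that demographics, religion and similar items explain, and leaves the rest.

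**The case against.** **The table error is clerical.** The anxiety-named instrument identifies itself, scoring follows the instrument, and the manual of operations may have the pairing right. This limits the consequence but does not remove the error. A protocol table that contradicts a correct manual still needs correcting, and the pairing is unchanged although rows were added to Table 3 between versions 1.0 and 1.8. A reader might infer that the data are compromised; the documents do not support that, because both scales are collected at every time point.

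**The covariate list is only illustrative.** It follows an initial comparison that does not use it, and section 5.3.2 speaks of association between outcomes and groups without stating an estimand. Nothing in the documents says that disclosure shifts genetic essentialism. All of this stands, so the reading that the adjusted result is biased by a known or material amount is not supported.

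**Attitudes may be genuine confounders.** The prospective controls declined sequencing (section 3.2.2.1), and attitudes may have influenced that choice. This also stands. It is why neither model should be ranked above the other, and why dropping the attitude scales outright would be wrong.

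**Part of the remedy is already planned.** Section 5.3 provides for adjustment when the groups differ in demographics or ultrasound severity. That is correct, although the adjustment is conditional on a difference being found.

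**Two further inferences go too far.** One is that the missing cut-off leaves the outcomes undefined. Section 5.3.2 allows continuous analysis, which needs no cut-off, and one may be set in the manual. The other is that genetic optimism is a covariate nobody collects; a slip for General Optimism is the simpler reading. Both are requests for clarification only.

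**Conclusion.** The pairing in Table 3 is an error and should be corrected. If followed, it misnames 6 secondary results; if not followed, it has no numerical effect. The conclusion rests on the instrument's own name in the Depression row, on the matching pairing in both protocol versions, and on the absence of any other mapping in the documents supplied.

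The covariate point holds in a smaller form. At least one of the three example covariates is scheduled only after disclosure in the sequenced group, so the adjusted contrast may understate or otherwise alter any disclosure effect. Its size cannot be derived from the documents and may be zero.

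Both parts concern secondary outcomes for which the current section 5.1 gives no power calculation. Neither primary outcome is touched, and the initial psychosocial comparison stands as planned.

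**What to change.** 1. Swap the two instrument entries in Table 3, and name the instrument in outcomes 6 and 7 of section 4.10.2.
2. In section 5.3.2, report the adjusted group contrast in two forms:
   - with covariates recorded at enrollment only: demographics including religion and religiosity; the ultrasound severity already compared under section 5.3; gestational age at diagnosis, derived from the ultrasound date and the estimated delivery date; and, for maternal outcomes, maternal psychiatric history;
   - with the post-disclosure attitude scales added, labelled as adjusting for variables measured after disclosure in the sequenced group.
3. State beside the first form that confounding by attitudes may remain.
4. As clarifications, say whether each scale is analysed as a score or by a cut-off (and which), and which Table 3 row genetic optimism refers to.

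**Cost.** Two table entries, two outcome lines, a few sentences in section 5.3.2 and one extra model per outcome and time point; no new data. Limits remain. Religion and religiosity cover attitudes only in part. Section 4.3 lists no paternal psychiatric history, so paternal outcomes cannot be adjusted for it. The documents define no severity measure, so the one used for the section 5.3 comparison must be named before it can serve as a covariate.

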#### 4.7.1 In-depth Qualitative Interviews

The impact of learning about the prenatal WGS test and return of prenatal WGS results will be evaluated by interviewing 45 sets of parents who were enrolled prospectively (90 participants) once between two weeks after result disclosure or four weeks after enrollment for participants in the unsequenced group and 15 months after delivery. Those willing to be interviewed will indicate this at the end of their psychosocial survey. Depending on the number of couples who volunteer for an interview, research staff will purposefully sample a range of parental ages, ethnicities, educational level, site, and fetal anomaly. Participants with positive or uncertain genetic test results and those who had difficulty adjusting to the information or were dissatisfied with participation in the study and have decision regret will be oversampled.

Both parents will be interviewed since men are often not included in these studies and are an integral part of the decision-making process and long-term outcome of the family. The interview data will be used to develop recommendations and identify factors associated with decision satisfaction, and to develop recommendations for pre- and post-test genetic counseling that reflect the needs of women and their partners as they make decisions about undergoing prenatal sequencing, or continuing a pregnancy after learning about a known or uncertain fetal sequencing abnormality.

# 4.8 Healthcare Utilization and Change in Management

Information on healthcare utilization and charges will be collected starting at the time of presentation to the hospital for delivery through discharge. Site coordinators will work with hospital billing to obtain detailed billing records from delivery admittance through discharge for each study participant, including the hospital charge ratio. Current Procedural Terminology (CPT) medical code, description, total units and total hospital charge will be collected. At the 12-month follow-up phone call for participants who were enrolled prospectively, information will also be recorded on healthcare utilization post neonatal discharge, including number of infant hospitalizations, surgeries, procedures and specialist visits. For twin gestations, this information will only be collected for the twin with the anomaly.

To identify if sequencing results changed the original care plan, the site coordinators will review all prenatal and postnatal medical records in conjunction with the designated physician from diagnosis until discharge or death to document change in healthcare management. Change in healthcare management will be completed by both the MFM/OB for prenatal assessment and a designated neonatal fellow in consultation with the clinical care team at each institution. The survey will include questions focused on clinical utility, such as: 1) have there been any changes to the patient's treatment plan based on the sequencing results, 2) have there been any changes to the way that you counsel the patient/family regarding the immediate medical management as a result of the sequencing results, and 3) have there been any changes to the way that you counsel the patient/family regarding the long term medical management as a result of the sequencing results. The changes in healthcare management will be presented and reviewed by the Clinical Adjudication Committee which will confirm whether an alteration in health care management occurred based on sequencing results.

# 4.9 Adverse Event Reporting

Detailed information concerning adverse events assessed to be definitely, probably or possibly related to study procedures will be collected and evaluated throughout the conduct of the study. Adverse events will be reported to the Data and Safety Monitoring Board.

# 4.10 Study Outcome Measures and Ascertainment

#### 4.10.1 Primary Outcome

- 1. Pathogenic, likely pathogenic, or VUS variants identified by sequencing and deemed reportable by the Variant Adjudication Committee
- 2. Maternal hospital charges between time of presentation to hospital for delivery to discharge, and neonatal hospital charges between delivery and infant discharge or death

#### 4.10.2 Secondary Outcomes (Prenatal sequencing and unsequenced prenatal)

- 1. Perinatal outcomes including gestational age at delivery, major morbidities including mechanical ventilation, sepsis, pressor support, ECMO, metabolic abnormalities (e.g., acidosis, elevated uric acid, hypo-/hyperglycemia), intraventricular hemorrhage, periventricular leukomalacia, encephalopathy, and seizure
- 2. Neonatal/infant death at time of discharge and at 12 months of age\*
- 3. Length of initial NICU stay and number of days spent in the hospital between initial discharge and 12 months of age\*
- 4. Infant weight and length at 12 months of age\*

- 5. Developmental parameters (communication, gross motor, fine motor, problem solving and personal-social) at 12 months of age using ASQ-3\*
- 6. Anxiety following result disclosure (or 4 weeks post enrollment for the unsequenced group), neonatal discharge and 12 months postpartum\*
- 7. Depression following result disclosure (or 4 weeks post enrollment for the unsequenced group), neonatal discharge and 12 months postpartum\*
- 8. Quality of life for the patient and family at 12 months postpartum\*
- 9. Incremental cost per Quality Adjusted Life Year (QALY)
- \* Only available on participants enrolled prospectively and followed through 12 months postpartum

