Prenatal sequencing has the potential to alter the life course and reduce morbidity and mortality by guiding pregnancy management, delivery plans and/or the treatment of fetuses and newborns with some genetic abnormalities. One example is *in utero* fetal intervention now performed for certain anomalies including aortic stenosis to avoid hypoplastic left heart syndrome, urinary diversion for posterior urethral valves, drainage of pleural effusions and chylothorax, surgical repair for spina bifida, tracheal occlusion for congenital diaphragmatic hernia, and amnio-infusion for renal agenesis. For all of these, knowing their genetic etiology aids clinical management decisions by providing information about other associated medical features that affect the likelihood of success of the intervention. In addition, prenatal diagnosis of some metabolic conditions could guide early postnatal treatment and avoid metabolic crises that can lead to long term neurocognitive deficits. For example, pyruvate dehydrogenase deficiency can present prenatally with structural anomalies and is modifiable by a ketogenic diet and thiamine supplementation. Finally, mesenchymal stem cell transplantation for osteogenesis imperfecta has been reported to increase skeletal mineralization and growth velocity without adverse outcomes. With developments in gene and stem cell therapy, this type of treatment may increasingly become an option for other conditions.

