#### 3.2.1.2 Exclusion Criteria

- 1. Imminent delivery planned (within 3 weeks of enrollment) as sequencing results would not be available prior to delivery
- 2. Prenatal sequencing or planned prenatal sequencing performed outside of the study. Gene panels may be performed prior to enrollment but the results must be known and negative to be eligible (positive or unknown results are an exclusion).

- 3. Maternal or paternal age less than 18 years old
- 4. Proven infectious, teratogenic, or other genetic cause of fetal anomaly
- 5. For twin gestation, anomalies in both fetuses (NT, IUGR, or structural anomaly)
- 6. Monochorionic diamniotic (MCDA) and monochorionic monoamniotic (MCMA) twins as well as higher-order multifetal gestations
- 7. Planned termination of the fetus or intrauterine fetal demise (IUFD)
- 8. Unavailable blood or saliva samples from both genetic parents prior to sequencing
- 9. Parental unwillingness to participate in 1 year postnatal follow-up
- 10. Language barrier (non-English or Spanish speaking)
- 11. Previous consent to the unsequenced prenatal group or enrollment in a previous pregnancy

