#### 3.2.3.2 Exclusion Criteria

- 1. Prenatal or postnatal (prior to neonatal discharge) CMA with pathogenic or likely pathogenic variants that are related to the prenatal ultrasound finding
- 2. Maternal or paternal age less than 18 years old
- 3. Proven infectious, teratogenic, or other genetic cause of fetal anomaly
- 4. Positive prenatal NIPT screening for trisomy 21, 18 or 13. Positive 22q11.2 prenatal NIPT testing with consistent ultrasound findings is also an exclusion.
- 5. For twin gestation, anomalies in both fetuses (NT, IUGR, or structural anomaly)
- 6. Monochorionic diamniotic (MCDA) and monochorionic monoamniotic (MCMA) twins as well as higher-order multifetal gestations.
- 7. Termination of the fetus or intrauterine fetal demise (IUFD) within 3 weeks of date of initial anomaly diagnosis
- 8. Language barrier (non-English or Spanish speaking)
- 9. Delivery at a site other than one of the study centers or associated hospitals
- 10. Unable to access prenatal or neonatal records

[figure not shown]

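### The only mortality outcome counts deaths after birth, so if sequencing results move some losses to before birth, mortality would look lower with no change in total loss

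*Combined protocol and SAP*

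**What the plan says.** All references are to Version 1.8.

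- **Event.** Section 4.10.2, outcome 2, is "Neonatal/infant death at time of discharge and at 12 months of age". The 12-month part is footnoted as available for prospective participants only.
- **Other between-group outcomes.** Outcome 1 reads "Perinatal outcomes including gestational age at delivery, major morbidities including mechanical ventilation, sepsis, pressor support, ECMO, metabolic abnormalities" and continues with further morbidities. The list is open-ended, but names no stillbirth, fetal death or termination. Neither do the other outcomes in section 4.10.
- **Comparison.** Section 5.3 compares pregnancy and neonatal outcomes between the sequenced group and the pooled unsequenced group. It excludes causal CMA findings made before neonatal discharge. It sets no denominator for mortality and no rule for a fetus lost after enrollment.
- **Later losses are foreseen.** Section 4.7 times the second survey at "One month after discharge from the hospital or end of the pregnancy if there is a fetal demise or pregnancy termination". Section 4.7.1 refers to parents "continuing a pregnancy after learning about a known or uncertain fetal sequencing abnormality".
- **Entry rules on loss.** In the two prospective groups, a termination planned at entry or a fetal demise at entry is an exclusion (3.2.1.2 and 3.2.2.2, item 7 in each). Retrospective controls are excluded for "Termination of the fetus or intrauterine fetal demise (IUFD) within 3 weeks of date of initial anomaly diagnosis" (3.2.3.2), and count as enrolled from the anomaly diagnosis (4.2.3).
- **Data.** Table 2 collects pregnancy complications and delivery outcomes in a row not marked prospective-only. Form PG07 covers delivery and neonatal outcomes to discharge.

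**The concern.** The exposure is a result delivered before birth, and the mortality outcome starts at birth. A liveborn infant who dies on day 1 is an event. The same fetus lost in utero after enrollment is not. Being born alive is itself a post-exposure event that the result may influence, through delivery planning or through decisions about the pregnancy. Appendix A admits anomalies such as anencephaly and body-stalk anomaly, and section 5.3 plans a lethal versus non-lethal subgroup, so such losses are not remote.

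At stake is the reading of the mortality comparison. Section 2.1 says that prenatal sequencing has the potential to "reduce morbidity and mortality by guiding pregnancy management, delivery plans and/or the treatment of fetuses and newborns" with some genetic abnormalities. A lower neonatal death rate would be taken as support for that, even if the only change were the timing of death relative to birth. The amendment history shows that the issue was recognised for charges: the reason given for that change is that fetal deaths generate no neonatal charges. The mortality outcome has no matching rule.

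**Working it through.** The plan gives no rate, sample size or power for mortality, so there is no stated figure to reproduce. What follows is an illustration.

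**Inputs from the plan.** 750 sequenced and 350 unsequenced (3.1); two-sided 0.05 (5.3).

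**Assumptions.** Per enrolled pregnancy, control fetal death f and neonatal death n are 2% and 10%, or 3% and 8%. Total loss f + n is the same in both groups. In the sequenced group, k points of death move from after birth to before birth.

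**Formulas.**
- Live births: RR = [(n − k)/(1 − f − k)] ÷ [n/(1 − f)]
- All enrolled: RR = (n − k)/n
- Chance of a significant result: normal approximation to the two-proportion test (pooled SE under the null, unpooled under the alternative).

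**One case in full** (2%/10%, k = 2, live births). Controls 0.10/0.98 = 10.20% of 343; sequenced 0.08/0.96 = 8.33% of 720; RR 0.82. The pooled proportion is 95/1063 = 8.94%, pooled SE 0.0187, unpooled SE 0.0193. Φ[(0.0187 − 1.96 × 0.0187)/0.0193] is about 0.18.

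| f / n | k | RR, live births | Chance | RR, all enrolled | Chance |
|---|---|---|---|---|---|
| 2% / 10% | 1 | 0.91 | 8% | 0.90 | 9% |
| 2% / 10% | 2 | 0.82 | 18% | 0.80 | 20% |
| 3% / 8% | 1 | 0.88 | 9% | 0.88 | 10% |
| 3% / 8% | 2 | 0.77 | 22% | 0.75 | 25% |

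Two points are 0.02 × 750 = 15 pregnancies. With about 300 controls, the number section 5.1 expects for the charges analysis, the chances are 8% to 23%.

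**Larger shifts.** k = 3 and 4 give live-birth RRs of 0.72 and 0.63 (first set) or 0.65 and 0.52 (second set), with chances of 35% and 58%, or 45% and 72%. Section 5.1 plans on a diagnostic yield of 9.4%. If only a diagnosis moves a death, k = 3 or 4 needs 3/9.4 = 32% or 4/9.4 = 43% of all diagnosed fetuses to have a death moved. For k = 1 or 2 the shares are 11% and 21%. The larger shifts are therefore upper-end scenarios.

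**Counting fetal plus neonatal death over all enrolled.** Both groups have f + n = 12% (or 11%), so RR = 1.00 for every k.

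**The termination route.** Suppose the k points move to termination instead.
- Composite over continuing pregnancies only: RR = [(f + n − k)/(1 − k)]/(f + n). For k = 3 this is 0.0928/0.12 = 0.77 (29% chance) or 0.0825/0.11 = 0.75 (32%).
- Composite over all enrolled, termination not counted: for k = 2 it is 0.10/0.12 = 0.83 or 0.09/0.11 = 0.82.
- Termination also counted as a loss: RR returns to 1.00.

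So a denominator of continuing pregnancies does not cure the problem, and an all-enrolled denominator closes this route only together with the termination-inclusive version.

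**The case against.** The strongest reply is that fetal loss already lies inside a planned comparison. Outcome 1 is an open list, section 5.3 compares pregnancy outcomes, and delivery outcomes are collected for all groups. That stands to this extent: a reader might infer that fetal deaths disappear from the study, and the documents do not support that. But fetal death is not named, and tabulating it elsewhere would leave outcome 2 as it is.

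Three further limits stand:

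- A reader might infer that mortality is defined among live births. No section says so. The bias does not depend on it, as the all-enrolled columns show.
- A reader might infer a high chance of a false mortality claim from the 35% to 72% figures. Those need the upper-end shifts, and every rate and shift is assumed. The direction is also conditional: sequencing is favoured only if deaths move to before birth more often in that group.
- The calculation applies to death by discharge. The 12-month part uses prospective participants only, and the amendment history says that prospective control enrollment was not feasible, so 750 versus 350 does not describe it.

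The stakes are also bounded. This is one unpowered secondary outcome, and the hypothesis in section 1.1 does not name mortality.

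**Conclusion.** The concern holds in a conditional form. The definition makes the mortality comparison depend on when a death falls relative to birth, and the plan itself foresees losses before birth and a route by which results could affect them. Under the two assumed pairs of control rates, a shift of 1 to 2 points gives a neonatal death RR of about 0.75 to 0.91 and an 8% to 25% chance of nominal significance, with no difference in total loss. The actual size is unknown, because the documents give neither rates nor any estimate of the shift. They do not support saying that a bias will occur, or that the study will claim a mortality benefit. They do support saying that neonatal death alone cannot establish one. The outcome definition should be changed before the comparison is made.

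**What to change.** Keep neonatal/infant death, and add to outcome 2 and section 5.3:

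1. **Composite.** Fetal plus neonatal death to discharge, compared between groups over all enrolled pregnancies left after the section 5.3 CMA exclusion. Pregnancies terminated after the start of counting stay in the denominator.
2. **Separate rows by group.** Fetal death, termination, neonatal death and survival to discharge.
3. **Sensitivity composite.** The same, with termination counted as a loss. It is a sensitivity analysis because it also counts terminated pregnancies that might have ended in survival.
4. **Common start.** Retrospective controls exclude losses in the first 3 weeks after diagnosis; the sequenced group has no such rule. Count losses in every group from the same point, for example 3 weeks after anomaly diagnosis or enrollment if later, among pregnancies ongoing then. List earlier losses separately, and report the time from diagnosis to start by group, since that may still differ.
5. **Interpretation.** State the denominator for every mortality figure, and draw no mortality-benefit conclusion from neonatal death alone.

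The cost is outcome and analysis wording plus a little more analysis. The delivery and neonatal data are already collected for all groups; the common start also uses the diagnosis and enrollment dates. The downside is a composite that mixes fetal and neonatal death, which is why its components must be shown.
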